4. STUDY SUMMARY

Study Title	Timing of Suture Removal to Reduce Scarring in Skin Surgery
Study Design	Prospective randomized assessor blinded parallel group feasibility study
Planned Size of Sample	60
Follow up duration	3 months
Research Question/Aim(s)	In patients undergoing wide local excision and primary wound closure for treatment of skin cancer, does earlier removal of percutaneous sutures (7 days rather than 10 days) reduce the incidence of suture marks assessed at 3 months post-operatively.

5. FUNDING

FUNDER	FINANCIAL AND NON FINANCIAL SUPPORT GIVEN
Dermatology Department Royal Devon and Exeter NHS Trust Heavitree Hospital	Financial support for printing patient information sheets and other required documentation. Facilitating space for clinic follow-up.

Timing of Suture Removal to Reduce Scarring in Skin Surgery

[name]	Support of the dermatology team helping with recruitment to trial.
Royal Devon and Exeter NHS Trust [name]	Support in the form of allocation of an academic foundation doctor as co-principle investigator.

6. ROLE OF SPONSOR AND FUNDER

Sponsor: Royal Devon and Exeter NHS Trust

Role of Sponsor:

- To take overall responsibility for the research
- Ensuring appropriate indemnity or insurance for the study
- Ensuring patient/participant safety and rights

Role of Funder:

- To aid in financial support for printing and dissemination of patient information sheets and postage of trial information to participants
- To provide healthcare professionals within the dermatology department to help with execution of patient recruitment and follow-up

8. TIMELINE

	Months			
	0	3-6	6-12	12-15
Finalize protocol	x			
Ethics submission	x			
Patient recruitment		x		
3 month follow-up			x	
Data entry			x	
Data analysis				x
Project write up				x

Timing of Suture Removal to Reduce Scarring in Skin Surgery

9. STUDY FLOW CHART

Timing of Suture Removal to Reduce Scarring in Skin Surgery

Timing of Suture Removal to Reduce Scarring in Skin Surgery

Protocol

Timing of Suture Removal to Reduce Scarring in Skin Surgery

10. BACKGROUND

A suture mark (also known as stitch mark or track mark) is scar tissue thought to be caused by local tissue necrosis following suture placement. The risk of suture marks appears to be associated with the timing of suture removal. Sutures left in situ for longer than seven days increase the risk of permanent scarring.

Percutaneous sutures are commonly used in dermatological surgery to achieve wound edge apposition, eversion and to prevent a depressed scar. Despite the risk of suture marks they are often left in situ for longer than seven days especially on sites of skin tension. On the chest or back it is common practice to wait up until 14 days before suture removal. The timing of suture removal is guided by surgeon preference and concern about wound dehiscence. However, wound dehiscence is unlikely to occur where there is adequate placement of dermal or subcuticular sutures (sutures beneath the top layer of skin, otherwise known as buried sutures). Where there is adequate subcuticular suturing to close the wound the percutaneous sutures may be removed earlier. There is currently no clear consensus on the timing of suture removal and the current standard of care varies between 7 and 14 days.

We hypothesize that earlier removal of percutaneous sutures (7 days rather than 10 days) reduces the incidence of suture marks in patients undergoing excision and primary wound closure for treatment of skin cancer. We are also interested to study whether early suture removal has an impact upon overall scar cosmesis, patient reported outcome measure, and wound complications including bleeding, infection, and dehiscence.

11. RATIONALE & LITERATURE REVIEW

Medline and CENTRAL were searched using the following terms “scar” and “skin” and (“suture” or “stitch”). 1585 titles were reviewed. 60 articles were identified for potential relevance and abstracts reviewed. 12 full text articles were reviewed.

Suture marks, sometimes described as ‘track marks’, ‘railroad tracks’, ‘cross hatching’ or ‘fishbone scars’ are a known complication of suture placement. The incidence of this occurrence and the impact on the patient is not known although they are seen as an unfavourable scar characteristic [1]. Surgical technique (tissue handling, suture technique, layered closure, use of lines of natural skin tension, close approximation and eversion) and patient factors (keloid tendency, skin type or body site) are thought to play an important role [2]. Another factor that is thought to play an important role is the timing of suture removal. Sutures left in place for more than seven days are thought to increase the risk of suture marks [3].

Percutaneous sutures are generally left in place for longer due to concern about wound dehiscence. However, several alternative wound closure techniques have been described to negate the use of percutaneous sutures or to reduce suture marks [4]. These studies demonstrate that adequate subcuticular suturing is sufficient for prevention of wound dehiscence. These include the use of adhesive glue following dermal closure with buried sutures [5], the use of buried subcuticular sutures alone [6], and suture removal and replacement of sutures at 3 days post operatively [7]. Another

Timing of Suture Removal to Reduce Scarring in Skin Surgery

study that assessed the use of adhesive strips following subcuticular running vertical mattress sutures found that adhesive strips provided no additional benefit to subcuticular sutures alone [8].

Despite alternatives to percutaneous closure, the use of percutaneous sutures is still common practice in dermatological surgery in the UK. This is because percutaneous sutures are considered best practice in order to achieve wound edge eversion and help prevent a depressed scar. There is insufficient evidence to guide the length of time until suture removal but common practice dictates that on sites of tension percutaneous sutures should remain in situ for longer until removal. On the chest or back suture removal between 7 and 14 days is normally suggested for suture removal.

Adequate approximation of the wound edges with placement of dermal sutures should negate the requirement for percutaneous sutures to remain in situ for longer than seven days even in sites of tension.

12. THEORETICAL FRAMEWORK

We are interested to assess whether earlier suture removal reduces stitch marks in wounds where close approximation of wound edges can be achieved with dermal sutures. In doing so we hope to provide evidence that earlier suture removal reduces the risk of suture marks without increasing wound complications.

As the incidence of suture marks is currently uncertain and the impact that these have on the patient is unknown we intend to perform a feasibility study prior to conducting a randomized controlled trial. This study would give an indication as to the sample size required to power our RCT correctly. It will also provide an indication as to the ease of recruitment, patient participation, loss to follow-up, and complication rate. Furthermore, it will allow us to evaluate the use of our chosen assessment tools.

We have designed a single centre, randomized, blinded, parallel group feasibility study to assess viability of a randomized control trial (RCT) to answer this question.

13. RESEARCH QUESTION

In patients undergoing wide local excision and primary wound closure for treatment of skin cancer does earlier removal of percutaneous sutures (7 days rather than 10 days) reduce the incidence of suture marks assessed at 3 months post-operatively.

Secondary questions:

Does earlier suture removal have an impact (negative or positive) on overall scar cosmesis and wound complication rates* (as assessed by the clinician and the patient)?

Timing of Suture Removal to Reduce Scarring in Skin Surgery

**Risk of post-operative bleeding, risk of surgical site infection, risk of wound dehiscence (opening up of scar)*

14. AIMS AND OBJECTIVES

Aim:

To test the feasibility of conducting a definitive trial looking at outcomes for earlier removal of percutaneous sutures (7 days versus 10 days) for patients undergoing wide local excision and primary closure for treatment of skin cancers on the chest or back in dermatology.

Objectives:

1. To work out the standard deviation of the outcome measure (suture marks versus no suture marks) in order to estimate a sample size required for a properly powered RCT. (The incidence of 'suture marks' and the impact that these have on patients is currently unknown).
2. To provide some preliminary data on the incidence of wound complications and overall scar cosmesis in each group and ensure that this does not differ from expected:
 - a. *Overall cosmesis*
 - b. *Risk of post-operative bleeding*
 - c. *Risk of surgical site infection*
 - d. *Risk of wound dehiscence (opening up of scar)*
3. To assess the willingness of participants to be randomized.
4. To assess the willingness of clinicians to recruit patients.
5. To assess follow-up rates and adherence.
6. To assess the characteristics and ease of use of the proposed outcome measures including POSAS for scar assessment, a VAS, and patient reported outcome for complications including dehiscence and infection.
7. To gain feedback from patients at their three month follow up appointment on the patient pathway including the trial information leaflet and consent process.
8. To collect data on any additional costs that we may incur that have not been planned for, to inform costing for a future trial e.g. additional printing of PIS or consent forms or additional clinic booking slots
9. To use the gathered data to refine the design of the proposed RCT.

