16.5 Wound Dressing and Post-operative Care

Following wound closure, the wounds will be dressed with steristrips, a sterile film and pad dressing as per protocol after skin surgery. After 48 hours, the patients will be instructed to remove the dressing and then gently cleanse the wound and apply petroleum jelly to it twice daily until suture removal. This advice will be given to all patients independent on which trial arm they have been allocated.

Timing of Suture Removal to Reduce Scarring in Skin Surgery

On the day of suture removal, either at GP or in the dermatology department, sutures will be removed as per our standard operating procedure (SOP), available in the department or emailed to the GP practice performing the suture removal (please see appendices).

If there are any signs of wound dehiscence, or that the wound may dehisce on suture removal, the suture may be kept in, as per advice on our SOP. These patients will be withdrawn from the study.

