18.4 Sample Size

As this is a feasibility study, it will not be powered to find significant differences between the groups. Instead it is an opportunity to test the feasibility of collecting the specified outcome data and describing it in terms of central tendency (mean, median) and dispersion (standard deviation or interquartile range as appropriate). A feasibility study provides an excellent opportunity to uncover problems ahead of time, minimizing the need to adapt procedures or to develop contingency plans at short notice when the larger study is being conducted. A simple method for choosing a sample size for a feasibility study that ensures the discovery of potential problems with high confidence is employed here [9]. The method is used to determine the necessary sample size so that a problem is likely to be observed at least once during the course of the feasibility study. The emphasis therefore is on “problem detection” and not on the estimation of the “problem frequency.” If the probability (p) of a problem arising is 0.05, then a sample size of 59 would be required to detect at least one instance of the problem. The formula for calculating this is approx. $3/p$ participants if one wants to be approximately 95% certain that the problem will manifest itself at least once during the feasibility study. We will aim for 30 analysable cases per group in the final dataset giving a total of 60 cases.

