19. ETHICAL AND REGULATORY COMPLIANCE

19.1 Patient Safety and Serious Adverse Events

A serious adverse event (SAE) is any untoward medical occurrence that:

- Results in death;
- Is life-threatening;
- Requires inpatient hospitalization or prolongation of existing hospitalization;
- Results in persistent or significant disability/incapacity;
- Consists of a congenital anomaly or birth defect.

Adverse events (AE) that may occur and for which patients will be consented include:

- Bleeding
- Infection
- Scarring
- Wound dehiscence
- Pain

We do not anticipate there being any increase in adverse events in either arm. The aim of the study is to assess whether early suture removal reduces scarring. It may become apparent that scarring is

Timing of Suture Removal to Reduce Scarring in Skin Surgery

less in the early suture removal arm. We will record the incidence of adverse events in both treatment arms to ensure that patients are not experiencing a greater number of adverse events in either treatment group

This is a pragmatic trial: the nature of the study means that it involves routine clinical practice. There should be no additional risk to patients beyond routine care. With good participant information and subsequent post-trial engagement, we would hope to recruit rapidly to the trial.

All AE's and SAE's will be reported to R&D within 24hrs of the investigator being made aware of the event. An SAE occurring to a participant will be reported to the REC that gave a favourable opinion of the study where the event was related or unexpected. This will be reported within 15 working days.

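### Objective 2 promises that complications will not differ from expected, which 30 patients per arm cannot show, and the withdrawal rule takes dehiscence cases out of the count it is meant to describe

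*Combined protocol and SAP*

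**What the plan says.** Section 14, objective 2, has two halves. The first is "To provide some preliminary data on the incidence of wound complications and overall scar cosmesis in each group". The second is to "ensure that this does not differ from expected". Items 2b to 2d name bleeding, surgical site infection and dehiscence.

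Section 19.1 says adverse events will be recorded in both arms "to ensure that patients are not experiencing a greater number of adverse events in either treatment group".

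Section 17 makes the analysis descriptive, rules out formal comparison of outcomes at this stage, and plans proportions with confidence intervals. Section 18.4 disclaims power for group differences, sizes the study for seeing a problem at least once and not for estimating how often it occurs, and adds: "We will aim for 30 analysable cases per group in the final dataset".

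Section 16.5 covers wounds that show dehiscence, or look likely to dehisce, when sutures are due out. The sutures may be kept in, and "These patients will be withdrawn from the study". Step 5 of the suture removal procedure (Appendix 13) likewise excludes patients whose sutures are kept in because the wound may dehisce, and asks the remover to tell the study team.

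**The concern.** There are two linked problems.

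First, the second half of objective 2 is an assurance. To check it one needs a reference rate, a rule for what counts as different, and enough patients to tell. The protocol has no reference rate and no rule, and 30 per arm is too few at most plausible rates. With no events or one event in an arm, the objective could be reported as met although a rate above 10% had not been excluded.

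Second, the withdrawal rule acts on one of the outcomes being described. Patients whose dehiscence is noticed at the removal visit can leave the study because of it, and the target is expressed in analysable cases. Nothing says that withdrawn patients stay in the complication tables. What is at stake is the dehiscence figure that would inform the design of the definitive trial (objective 9).

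**Working it through.** **Inputs.** 30 per arm, 60 in total, problem probability p = 0.05 and about 95% certainty (section 18.4). The documents give no expected complication rate and no margin, so the rates and counts below are assumptions. The 5% rate matches the protocol's own p.

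**1. The plan's own figure.** n = ln(0.05)/ln(1 − 0.05) = 58.4, so 59; the approximation 3/p gives 60. Section 18.4 reproduces. The chance of at least one event at p = 0.05 is:

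- 60 patients: 1 − 0.95^60 = 95.4%
- one arm of 30: 1 − 0.95^30 = 78.5%

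Objective 2 speaks of each group. Within one arm, 95% certainty of seeing an event needs a true rate of at least 1 − 0.05^(1/30) = 9.5%.

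**2. Precision in one arm (Clopper-Pearson, two-sided 95%).** For no events the upper limit is 1 − 0.025^(1/n). At n = 30 this is 11.6%.

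| Events in 30 | 95% interval |
|---|---|
| 0 | 0 to 11.6% |
| 1 | 0.1 to 17.2% |
| 2 | 0.8 to 22.1% |
| 3 | 2.1 to 26.5% |

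**3. Precision of the difference (Newcombe).** For 1/30 in each arm the Wilson limits are 0.6% and 16.7% around 3.3%. The half-width is √(0.0274² + 0.1334²) = 0.136, so the interval is −13.6 to +13.6 points. With 0/30 in each arm it is about ±11.4 points.

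**4. What excluding an excess would need.** With equal true rates p, margin m, one-sided 2.5% and 80% power, n per arm = 7.849 × 2p(1 − p)/m².

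| True rate | m = 10 points | m = 5 points |
|---|---|---|
| 2% | 31 | 124 |
| 5% | 75 | 299 |
| 10% | 142 | 566 |

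Only a 10-point margin at a 2% rate comes close to 30 per arm, and the protocol sets no margin.

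**5. Effect of the withdrawals on dehiscence.** Suppose d of n patients in an arm dehisce, and w are withdrawn, e of whom dehisce. The reported proportion is (d − e)/(n − w). It falls below d/n whenever e/w > d/n, that is, when dehiscence is more common among withdrawn patients than in the arm as a whole. The rule selects on dehiscence, so that is to be expected. Illustration with n = 30 and every dehiscence withdrawn (counts assumed):

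| Dehiscences | All randomised | Withdrawn left out |
|---|---|---|
| 1 | 1/30 = 3.3% | 0/29, upper limit 11.9% |
| 2 | 2/30 = 6.7% | 0/28, upper limit 12.3% |
| 3 | 3/30 = 10.0% | 0/27, upper limit 12.8% |

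In each row the reported rate is zero.

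**The case against.** The best defence is that the protocol claims little. Objective 2 begins with preliminary data, section 12 speaks only of an indication of the complication rate, and sections 17 and 18.4 openly disclaim power and comparison. Intervals for proportions are already planned, so a count of 0/30 would appear with its upper limit. All of this stands, and it makes the point one of wording and of who is counted. It does not rescue the second half of objective 2, which is a separate undertaking with no reference value and which those same sections contradict.

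A reader might take section 19.1 as a claim of equal safety between arms. It reads more naturally as monitoring: it stands under patient safety, beside 24-hour reporting to R&D. Recording events in order to watch for an excess is not an inferential claim.

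On withdrawals, the defence is that the cases are not invisible. Appendix 13 asks removers to report kept sutures and early dehiscence, infection or poor healing, and section 19.1 sends all adverse events to R&D. That is right, and it means the data can be recovered. It does not place these patients in the objective 2 tables.

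**Conclusion.** The point holds as an overstated objective together with an undefined denominator. Thirty per arm leaves an upper limit of 11.6% after no events and ±13.6 points after one event in each arm. These figures are a best case, since the 60 prepared envelopes leave no allowance for withdrawals. The understatement of dehiscence rests on withdrawn patients being left out of the tables, which is how the text reads if followed as written. Its size cannot be given, because no dehiscence rate or withdrawal rate is stated.

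Three stronger conclusions might be inferred, and the documents do not support them:

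- **That bleeding and infection counts are also pushed towards zero.** The rule concerns actual or threatened dehiscence. For infection, the procedure asks for medical advice and notification, not withdrawal.
- **That a definitive trial would start on false reassurance.** No progression rule depends on objective 2, and section 20 says only that a grant proposal may follow.
- **That the sample size calculation is wrong.** It reproduces, for the purpose it states.

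**What to change.** 1. **Objective 2.** Reword along these lines: *estimate the incidence of each complication in each arm with an exact 95% confidence interval, counting all randomised patients, including those whose sutures were left in and who are withdrawn from the scar assessment.* Delete the clause on expected rates, or state the expected rate for each complication and its source.
2. **Section 17.** Say that complications notified under Appendix 13 or reported under section 19.1 enter the outcome tables. Show actual dehiscence separately from sutures kept in because dehiscence was feared, so that the second is not coded as the first.
3. **Section 17 or 18.4.** State that few or no events will not be read as evidence of equal safety, giving the 11.6% limit for 0/30.
4. **Section 19.1.** At most, soften *ensure that* to *monitor whether*.

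The cost is wording, a few more patients in the complication tables, and a less favourable stated aim. The patient information should be checked to confirm that complications may still be recorded after withdrawal from the scar assessment. No change to suture removal or other clinical management is proposed.

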15. LAY SUMMARY

Stitch marks (also known as suture marks or track marks) are permanent marks left in the skin where the stitch has caused local tissue damage and scarring. The risk of these marks is in part thought to be related to the length of time that the stitches are left in place before removal. Stitches are normally left in place for longer on sites where the skin is under greater tension such as the chest or back because there is a concern that the wound may be more likely to open up on these sites. On

Timing of Suture Removal to Reduce Scarring in Skin Surgery

the chest or back, stitches may be left in place for up to 14 days even though the chest or back is a common site for stitch marks to form.

In skin surgery, wounds are commonly closed in two layers. A layer of dissolving stitches is placed under the top layer of the skin to bring the wound edges together. These stitches do not need to be removed. Another layer of stitches is then placed along the top of the wound, often with non-dissolvable stitches that need to be removed. If the wound edges can be brought closely together with the deeper stitches, then we do not believe that the top stitches need to stay in place for longer than seven days, even on sites of tension. This is because the deeper stitches should prevent the wound from opening up. We believe that stitch removal at 7 days rather than 10 days reduces the risk of stitch marks without increasing the risk of the wound opening up.

We would like to perform a small study to assess how practical it will be to perform a full study to look at whether earlier removal of superficial stitches (7 days rather than 10 days) reduces the risk of stitch marks.

We would also like to assess the impact that stitch marks have on patients, the effect of early stitch removal on the overall appearance of the scar, and the effect of early stitch removal on the number of wound complications.

We aim to invite patients to join the study who are having a wide local removal of skin on the back or chest. These patients will be randomly assigned to two groups: stitch removal at 7 days and stitch removal at 10 days. The two groups will otherwise be treated the same. Patients will be reviewed again at 3 months to assess their scar and the presence of stitch marks, and to record information about any complications they experienced and information about their experience. This information will be used to assess the feasibility of a larger study to answer the question 'does earlier removal of superficial stitches (7 days rather than 10 days) reduce the risk of stitch marks?'

